**8.8.5 Study Drug Accountability**

The study drug provided is for use only as directed in this protocol.

The Investigator must keep a record of all study medication received, used and discarded. It must be clear from the records whether the subject received study medication or was assigned to standard of care. Adequate drug is to be dispensed for the number of subjects expected to be treated at each institution.

The pharmacist/staff member responsible for drug accountability is to document the date and time of dispensing and for what subject the study drug was intended (i.e., record subject initials and birth date or other unique identifier). A pharmacy manual will be provided by the Sponsor.

Subjects in the brequinar group who are discharged prior to Day 5 will be given a study medication diary for recording at home treatment administration. The diary information will be collected by

PROTOCOL NUMBER: CCB-CRISIS-01  
PROTOCOL VERSION FINAL DATE: 10SEPT2020

Page 32 of 58

the study team either verbally or electronically or in person during a visit to the research facility. Unused study drug at the patient's home is to be returned to the research facility.

At the end of the study, any unused study drug in the pharmacy will be returned to the Sponsor for destruction or may be destroyed locally; disposition of study drug will be documented. The study team will make arrangements for the subject to return any unused study medication to the research facility.

The Sponsor will be permitted access to the trial supplies at any time within usual business hours and with appropriate notice during or after completion of the study to perform drug accountability reconciliation. Records may be electronic or paper and may be accessed remotely for monitoring/drug accountability purposes.

### **8.9 Prohibited Medications**

Treatment is prohibited with another DHODH inhibitor (e.g., leflunomide and teriflunomide), tacrolimus, sirolimus. Treatment is prohibited with agents known to cause bone marrow suppression leading to thrombocytopenia.

### **8.10 Study Adjustments Due to COVID-19**

Due to the highly contagious nature of COVID-19, multiple adjustments and revised procedures are rapidly evolving regarding clinical trial management and study conduct. Reasonable procedures implemented by study staff to avoid spreading this disease are acceptable to Clear Creek with written permission. Examples include but are not limited to e-consent, telephone consent and study visits conducted by telephone or other digital media. Study information is to be collected from the EHR as much as possible such as NEWS2 Assessments, height, weight, hematology/chemistry, from Progress Notes for AEs, and from medication records for new or changed concomitant medications. Visits to an outpatient laboratory post hospital discharge may be required if subjects are not able or permitted to return to the research facility for follow up study visits.

Background standard of care is to be maintained in both treatment arms. The standard of care is expected to change as additional information, such as that from randomized controlled trials, emerges, and the Sponsor and the treating clinicians will need to address anticipated off-label use of any other drugs, devices, or interventions that might be used to manage COVID-19 (e.g. anticoagulants). Remdesivir may be used in this clinical trial as a component of standard of care of patients hospitalized with severe disease in settings where remdesivir is available via the Emergency Use Authorization (EUA) or other FDA approval.

The Sponsor and treating clinicians are to consider changes in SOC over time, for example, overlapping toxicities of brequinar and a SOC treatment expected to be widely used is to be considered. The availability of new standard of care treatment may change over time and vary from one clinical trial site to another. The Sponsor will discuss these issues with FDA should the need arise.

## **9 CONDUCT OF THE TRIAL**

### **9.1 Ethical and Regulatory Considerations**

The trial will be performed in accordance with the Declaration of Helsinki (1964) as revised in Tokyo (1975), Venice (1983), Hong Kong (1989), South Africa (1996), Scotland (2000, Note of Clarification 2002 & 2004) and Seoul 2008 (Appendix A), and Fortaleza (Brazil) (2013), and with the International Council on Harmonization (ICH) Tripartite Guideline on Good Clinical Practice (CPMP/ICH/135/95, Jan.97) and United States (US) FDA Regulations.

### **9.2 Informed Consent**

The principles of informed consent in the current edition of the Declaration of Helsinki must be implemented in each clinical study before protocol-specified procedures are carried out. Informed consent must be obtained in accordance with US Code of Federal Regulations (21 CFR Part 50), the FDA Guidance on Conduct of Clinical Trials of Medical Products during the COVID-19 Public Health Emergency (March 2020, Updated April 16, 2020), as well as local and national regulations. Information should be given in both oral and written form whenever possible and deemed appropriate by the Institutional Review Board (IRB). Subjects and their relatives, if necessary, must be given ample opportunity to inquire about details of the study.

The Investigator or qualified designated person will verbally inform subjects as to the nature, expected duration and purpose of the trial, the administration of the Investigational Product (IP), and the hazards involved, as well as the potential benefits that may come from treatment with this IP. The trial procedures will be explained in lay language and any questions will be answered. The subjects will be given an IRB-approved consent form. The subjects will be given appropriate time to consider their participation in the trial and have any questions answered prior to signing the consent form. If a subject agrees to participate, he/she will sign and date an informed consent form and be provided with a copy of the signed consent. All subjects who sign an informed consent form are to be recorded on the applicable screening log. If the subject is unable to consent for any reason, a designated family member or healthcare power of attorney or other person may consent per institutional policy.

The subject will be informed that his/her medical records will be subject to review by the Sponsor, Sponsor's representatives, and possibly by a representative of the FDA and other relevant regulatory authorities. Subjects will be informed that they are free to refuse participation in this clinical investigation, and if they should participate, it will be made clear to them that they may withdraw from the trial at any time without prejudicing further medical care they may require. The subject will receive a copy of the consent form as well as an information sheet about the trial.

Signed written informed consent must be obtained from every subject prior to any study-specific procedures. Standard procedures carried out prior to signing the informed consent but within the time constraints of the protocol may be used for baseline evaluation; they need not be repeated. An original signed informed consent form will be subject to review by the Sponsor; a copy will be given to the subject and a copy will be filed with the subject's medical notes.

Note that informed consent procedures have been affected by COVID-19, and the study staff may use any consent method that has been approved by the IRB (e.g., phone consent, verbal consent

PROTOCOL NUMBER: CCB-CRISIS-01  
PROTOCOL VERSION FINAL DATE: 10SEPT2020

Page 34 of 58

with witness, e-consent, etc.) of the local institution. In-person consent, written consent signatures and providing hard copies to the subject are examples of procedures that may be foregone under these circumstances.

The study should be discussed with the potential participant only after an initial review of his/her clinical status and appropriateness for participation have been evaluated to determine if he/she meets the subject selection criteria.

A sample subject information sheet and consent form are available from Clear Creek. The final version at each institution may differ depending on institutional requirements and standard formats. This protocol will not be amended for site specific changes.

### **9.3 Institutional Review Board**

It is the responsibility of the Investigator to submit the protocol, consent form and information sheet to the IRB. An IB will be available for review by the IRB. The protocol and informed consent form (ICF) must be approved by the IRB prior to the recruitment of the first subject. The template consent form may be revised in accordance with site-specific requirements with Sponsor review and approval. A copy of the IRB written approval must be provided to the Sponsor and investigator before the trial may start at that institution. Written approval from the IRB is also required for substantial protocol amendments prior to their implementation.

A substantial amendment may arise from changes to the protocol or from new information relating to the scientific documents in support of the trial. Amendments are “substantial” when they are likely to have an impact on:

- the safety or physical or mental integrity of the subjects;
- the scientific value of the trial;
- the conduct or management of the trial; or
- the quality or safety of any IP used in the trial.

If it is necessary to change or deviate from the protocol to eliminate an immediate hazard to the subjects, the Investigator will notify the Sponsor and the IRB of the new events and the measures taken as soon as possible.

The Investigator will report promptly to the Sponsor and IRB any new information that may adversely affect the safety of the subjects or the conduct of the trial. On completion of the trial, the Investigator will inform the applicable IRB as per local IRB requirements that the trial has ended. If the study is terminated for any reason, the investigator will return all clinical supplies and study-related equipment supplied by the Sponsor to the Sponsor unless otherwise specified.

### **9.4 Schedule of Events**

NEWS2 Assessments, laboratory assessments, SARS-CoV-2 testing, and other observations will be conducted by experienced personnel throughout the study based on the Schedule of Events. The majority of study information is to be collected from the EHR. Phone calls or other digital media and outpatient visits for hematology/chemistry samples may be required to complete some study assessments if the subject is discharged prior to Study Day 15.

PROTOCOL NUMBER: CCB-CRISIS-01  
PROTOCOL VERSION FINAL DATE: 10SEPT2020

Page 35 of 58

See [15.1 Schedule of Events in Appendix A](#) for the full list of study assessments and timings.

Blood chemistry tests include blood urea nitrogen (BUN), creatinine, alkaline phosphatase (ALK), alanine amino transferase (ALT), aspartate amino transferase (AST), bilirubin, total protein, albumin, glucose, serum electrolytes (sodium, potassium, chloride, carbon dioxide/bicarbonate, and calcium), lactate dehydrogenase (LDH).

Inflammatory markers including D-dimer, ferritin, CRP, ESR, troponin, fibrinogen, and procalcitonin may be collected locally if available by the Institution. Additional inflammatory markers will be collected and analyzed by a central laboratory, as specified in the Laboratory Manual. A sample is to be collected for DHO and brequinar pharmacokinetics at the timepoints specified in the Laboratory Manual.

Hematology tests include hemoglobin, hematocrit, complete blood count with full differential, and platelet count.

If urinalysis is clinically indicated, collect results from the EHR.

Nasopharyngeal swabs for SARS-CoV-2 viral load, inflammatory markers, and DHO samples will be collected Days 1, 3, 5, 7, and 15 (standardized collection instructions available in the supplied Laboratory Manual; please use the same nostril each time). Samples may be banked for future retrospective analyses.

NEWS2 Criteria are available in [Appendix C Section 15.3](#).

Hospitalization status is to be recorded as hospitalized not in ICU, hospitalized in ICU, or discharged.

## 9.5 Study Conduct

### Screening Visit (Since hospital admission)

These procedures must be completed since hospital admission and prior to starting dosing. Obtain the subject's written informed consent (be sure to note time of consent), then collect baseline information from the EHR. Do not perform study specific procedures for data available from the EHR. For Screening/Day 1 use the EHR results closest to the visit to confirm subject eligibility.

- Demographics (date of birth, gender, race, ethnicity, height and weight).
- Recent (within one year unless ongoing), relevant medical/surgical history and concomitant medications.
- Date of first symptom.
- Record any new or changed adverse events and new or changed concomitant medications since signing the ICF.
- Record any clinically significant abnormal physical examination findings as recorded in EHR.
- Hematology/chemistry from EHR.

PROTOCOL NUMBER: CCB-CRISIS-01  
PROTOCOL VERSION FINAL DATE: 10SEPT2020

Page 36 of 58

- Ensure negative pregnancy test result is present in the EHR for women of childbearing potential (WOCBP).
- Polymerase chain reaction (RT-PCR) or other FDA-cleared commercial or public health assay for SARS-CoV-2 infection (may utilize test results from external laboratory to meet entry criteria provided such results are accurately documented and can be confirmed).
- Confirm subject meets all inclusion and no exclusion criteria.

## Treatment

The treatment period is up to 5 days: standard of care alone (SOC) or SOC + brequinar 100 mg daily for 5 days. Data points such as NEWS2 Assessments are to be collected from the EHR when possible, a separate visit by study staff is not to be conducted. The first dose of brequinar is to be given as soon as possible depending on availability of investigational pharmacy staff. If the subject is discharged from the hospital prior to Day 15, see [Section 8.5](#) for how and when to conduct study assessments.

It is understood that some assessments may not be conducted if the subject is unable to return to the clinic after discharge due to restricted travel or if the study visit cannot be conducted remotely; this will not be counted as a protocol deviation. Collect information from the EHR, medication records and Progress Notes whenever possible

### Days 1 - 7 (8 AM ± 8 hours)

- If Day 1 is a different date from Screening, confirm subject continues to meet all inclusion and no exclusion criteria.
- Randomize the subject (record date and time of randomization).
- Review Progress Notes and medication records to collect any new or changes to ongoing adverse events or new or changed concomitant medications since previous visit (may be omitted on Day 1 if Screening visit was conducted on same day as Study Day 1). Repeat daily until discharge.
- Collect SOC hematology/chemistry results from the EHR beginning on Day 1 (pre-dose) (may be omitted for Day 1 if Screening visit conducted on same date as Study Day 1) then daily through Day 7 or until the clinician decides daily testing is no longer necessary. Ensure that Day 1 samples are obtained prior to first dose of study drug, if applicable.
- Days 1 (pre-dose), 3, 5, 7:
  - Collect NEWS2 Assessments from the EHR.
  - Collect results for inflammatory markers from EHR for those analyzed locally; collect, process and ship samples for DHO/brequinar PK and cytokine panel to be analyzed at the central laboratory per the Laboratory Manual.
  - Collect and process SARS-CoV-2 nasopharyngeal viral load samples.
  - Record hospitalization status (hospitalized, hospitalized in ICU, discharged) (Day 1 already recorded as part of Inclusion criteria, do not record again).
- Dispense study medication (Days 1 through 5 if in brequinar group) and record date and time of brequinar administration. Keep the drug administration interval as close as possible

PROTOCOL NUMBER: CCB-CRISIS-01  
PROTOCOL VERSION FINAL DATE: 10SEPT2020

Page 37 of 58

to 24 hours. Ensure Day 1 labs are drawn prior to first brequinar dose on Day 1. If a subject taking brequinar is discharged prior to Day 5, give the subject adequate study drug to take home along with a diary to record daily treatment administration through Day 5.

- Drug accountability Day 7  $\pm$  2 days.

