Investigational Product and Dosage	
Subjects will be randomized in a 1:2 ratio to either standard of care (SOC) alone, or SOC + brequinar.
 
Brequinar is available as 100 mg oral capsules. Five once daily doses of brequinar 100 mg are to be administered on Study Days 1 – 5 for those assigned to the SOC + brequinar group.

	Treatment assignment will be randomized, open label.
Primary Objective	
 
To determine the safety and tolerability of SOC and SOC plus brequinar in hospitalized COVID-19 subjects.
 

Secondary Objectives	
 
To determine the rates of/changes in clinical status measures listed through Day 15:                             
 
Hospitalization status
 
Duration of hospitalization
 
NEWS2 Score
 
 
 
Mortality through Day 29
 

Exploratory Objectives	
 
To determine the change in SARS-CoV-2 nasopharyngeal viral load through Day 15
 
To determine the change in inflammatory markers through Day 15
 
To determine the change in DHO levels through Day 15
 
To determine the change in brequinar concentration levels through Day 7
 

Design	
This will be a phase 1a randomized, open label, multi-center study with approximately 24 subjects. All subjects will receive SOC per institutional guidelines for treatment of patients with COVID-19 infection. In addition to SOC, the brequinar group will receive brequinar 100 mg once daily for 5 days.
 
Subjects will have a Screening Visit followed as soon as possible with Study Day 1 (Day 1 may take place on the same day if entry criteria data are available). Study procedures are presented in detail in the procedures section, see below. Subjects will be followed through Day 15. Mortality will be assessed at Day 29.
 
See below for instructions regarding hospital discharge prior to Day 15.
 
Hematology and chemistry results and study information such as NEWS2 criteria are to be collected using the available EHR data as much as possible to avoid extra procedures for the study.

Sample Size:	Approximately 24 subjects will be randomized to either standard of care or standard of care plus brequinar in a 1:2 ratio (approximately 8 assigned to standard of care and 16 subjects on brequinar).
Number of Sites:	1 - 8
Study Period:	An enrollment period of 3 months is expected.

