	
external laboratory to meet entry criteria provided such results are accurately documented and can be confirmed).
 

• Confirm subject meets all inclusion and no exclusion criteria.

 
Treatment
 
The treatment period is up to 5 days: standard of care alone (SOC) or SOC + brequinar 100 mg daily x 5 days. Data points such as NEWS2 Assessments and safety labs are to be collected from the EHR, a separate visit by study staff is not to be performed. Give the first dose of brequinar as soon as possible after randomization. See below regarding hospital discharge prior to Day 15.
 
Days 1 – 7 (8 AM ± 8 hours):
 

• If Day 1 is different date from Screening, confirm subject continues to meet all inclusion and no exclusion criteria.

• Randomize subject and record the time and date of randomization.

• Review Progress Notes and medication records to collect any new or ongoing adverse events or new or changed concomitant medications since previous visit (may be omitted on Day 1 if Screening visit is conducted on same day as Study Day 1). Repeat daily through hospital discharge.

• Collect SOC hematology/chemistry results from EHR on Day 1 (pre-dose) (may be omitted for Day 1 if Screening visit conducted on same date as Study Day 1) then daily through Day 7 or until the clinician decides daily testing is no longer necessary. Ensure that Day 1 samples are obtained prior to first dose of study drug, if applicable.

• Days 1 (pre-dose), 3, 5, 7:

– Collect NEWS2 Assessments from EHR.

– Collect results for inflammatory markers from EHR for those analyzed locally; collect, process and ship samples for DHO/brequinar PK and cytokine panel to be analyzed at the central laboratory per the Laboratory Manual.

– Collect, process, and ship nasopharyngeal viral load samples.

– Record hospitalization status (hospitalized, hospitalized in ICU, discharged); subject must be hospitalized Day 1 to meet inclusion criteria, do not record again.

• Dispense study medication (Days 1 through 5 if in brequinar group). Keep the brequinar study drug administration interval to 24h as much as possible. Record date and time of study drug administration.

• Drug accountability Day 7 ± 2 days.

 
Final Visit Day 15 (8 AM ± 2 days)
 

• Review Progress Notes and medication records to collect information for any new adverse events or changes in ongoing adverse events or new or

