## **6 TRIAL ENDPOINTS**

### **6.1 Primary Endpoint**

- Safety/tolerability measured by rates of post randomization adverse events and hematology/chemistry safety labs.

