#### 8.4.2 Study-Level Stopping Criteria

Following assessment by the Data Safety Monitoring Board (DSMB, see [Section 10.9](#)), the study is to be stopped as shown below:

- If  $\geq 4$  subjects on the brequinar treatment arm develop the same Grade 3 or 4 adverse event or symptomatic laboratory abnormality
- If  $\geq 8$  subjects on the brequinar treatment arm develop any Grade 3 or 4 adverse event or symptomatic laboratory abnormality.

### 8.5 Hospital Discharge Prior to Study Day 15

Subjects discharged from the hospital prior to the Day 15 visit are to return to a research facility when feasible for the remaining study visits. All scheduled study assessments are to be completed at these visits when conducted at a research facility.

PROTOCOL NUMBER: CCB-CRISIS-01  
PROTOCOL VERSION FINAL DATE: 10SEPT2020

Page 30 of 58

For subjects in the brequinar treatment group discharged from the hospital prior to Day 5, the subject is to take home the remaining doses of brequinar for daily self-administration. All subjects (brequinar and SOC) should have the scheduled assessments, e.g. lab samples and the nasopharyngeal swab, on the day of discharge and enter these results on the appropriate EDC page. Following discharge, subjects are to return to the research or out-patient lab collection facility for the remaining study visits, if feasible. Out-patient lab results are to be entered into the EDC and reviewed by a member of the study team. It is important that every effort be made to have subjects return at least on Days 7 and 15, if feasible. Subjects in the brequinar group are to record brequinar dosing on the medication diary provided by the study team. The study team will arrange for the subject to return any unused study medication to the research facility.

For all subjects, if discharge occurs on Days 10, 11, or 12, ensure a hematology/chemistry sample has been obtained on the day of discharge and record these results on the appropriate EDC page. Following discharge, the subject is to return to the research or out-patient lab collection facility for the Day 15 visit, if feasible. Out-patient lab results are to be entered into the EDC and reviewed by a member of the study team.

If discharge occurs on Days 13, 14 or 15, complete the Day 15 Final Visit activities prior to discharge. No further visits are required unless follow up is needed for a study drug-related AE or an SAE; the Day 29 mortality assessment is still to take place.

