#### **Final Visit Day 15 (8 AM $\pm$ 2 days)**

- Review Progress Notes and the medication record to collect information for any adverse events or new concomitant medications since Day 7 (from EHR if subject still hospitalized, otherwise by phone or other digital media).
- Collect results for SOC hematology/chemistry from the EHR if subject still hospitalized.
- Collect inflammatory markers from EHR for those analyzed locally; collect samples for DHO and cytokine panel to be analyzed at the central laboratory if subject still hospitalized.
- Collect NEWS2 Assessments from the EHR.
- Collect nasopharyngeal viral load sample.
- Collect hospital status (hospitalized, hospitalized in ICU, discharged).

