### **10.8 Safety Monitoring for Hematologic Toxicities**

Myelosuppression is a known effect of DHODH inhibition that is associated with prolonged exposure and high doses. To reduce the risk of this effect with brequinar in COVID-19 subjects, the extensive brequinar safety database with over 1,000 patients has been evaluated to select a dose level expected to be safe and well tolerated with regard to hematologic toxicity. In addition to enhancing safety by selecting a relatively brief 5-day exposure and a low brequinar dose, all subjects in the clinical trial will initially be hospitalized as in-patients and will be under the care of highly qualified infectious disease, critical care, and associated medical personnel. As is standard of care for moderately to severely ill in-patients, daily samples will be obtained for hematology assessments including complete blood count with full differential (WBC, RBC, hemoglobin, hematocrit, platelet count, absolute neutrophils, absolute lymphocytes, absolute monocytes, absolute eosinophils, and absolute basophils). Any clinically significant out-of-range laboratory values will be assessed by hospital staff in a timely manner and treatment needs addressed as appropriate. Clinically significant out-of-range laboratory results will be reported as adverse events.

In addition to real time assessments by the treating clinical team, the Clear Creek Medical Monitor will assess the available hematology data on a weekly basis to identify any pathologic trends or safety issues. Any apparent increase in the expected rate or severity of hematologic safety events will be discussed with the Principal Investigators, the Sponsor, and the Medical Monitor. In addition, the Data Safety Monitoring Board will assess available hematology data on a periodic basis to independently assess any pathologic trends or safety issues. If the rate or severity of hematologic toxicities appears to be above the expected rate or the severity appears worse than that expected, the trial enrollment will be suspended and no further subjects will be treated while a comprehensive data review is conducted. Depending on the outcome of the safety review the study may be stopped, the design adjusted, or the study may continue as designed. Individual and study stopping rules are provided in [Section 8.4](#).

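### For subjects who stay in hospital, routine hematology/chemistry has no scheduled collection between Day 7 and the Day 15 visit, so the laboratory component of the primary endpoint cannot describe a transient fall in counts on Days 8-14

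*Protocol*

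**What the plan says.** All references are to the current version, dated 10 September 2020.

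- **Endpoint.** Section 6.1 defines the primary endpoint as "Safety/tolerability measured by rates of post randomization adverse events and hematology/chemistry safety labs".
- **Dosing.** Synopsis: "Five once daily doses of brequinar 100 mg are to be administered on Study Days 1 – 5".
- **Labs to Day 7.** Section 9.5, Days 1-7: results are taken from the electronic health record on Day 1 before dosing, "then daily through Day 7 or until the clinician decides daily testing is no longer necessary". The synopsis says the same.
- **Labs at Day 15.** Section 9.5: "Collect results for SOC hematology/chemistry from the EHR if subject still hospitalized". The visit is headed "Final Visit Day 15 (8 AM ± 2 days") in the synopsis. The Schedule of Events in Appendix A agrees: Days 1-7, then one entry at Day 15.
- **Safeguard.** Section 10.8: "As is standard of care for moderately to severely ill in-patients, daily samples will be obtained for hematology assessments". The same section has the Medical Monitor look weekly at whatever hematology data are available, and has the DSMB do so periodically.
- **Discharge.** Section 8.5, both arms: "if discharge occurs on Days 10, 11, or 12, ensure a hematology/chemistry sample has been obtained on the day of discharge". And: "If discharge occurs on Days 13, 14 or 15, complete the Day 15 Final Visit activities prior to discharge". Section 3.9 separately asks for a discharge-day sample from any brequinar subject who leaves before completing the study.
- **Adverse events.** These are reviewed daily until discharge, reviewed again at Day 15 for the period since Day 7, and collected through Day 15 (Sections 9.5 and 10). Section 10 limits when a laboratory value counts as an adverse event: it must cause signs or symptoms, be considered clinically significant, or need therapy.

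**The concern.** The collection rule and the safety argument do not match. Section 10.8 presents daily in-patient counts as a protection against myelosuppression, but the instruction to record those counts stops at Day 7, two days after the last scheduled dose. The instructions for adverse events in the same section do not stop there. Staff therefore open the Days 8-14 chart of a continuing in-patient to look for events, but are not asked to record the platelet, neutrophil or hemoglobin values they find in it.

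At stake is how well the laboratory component can describe the toxicity of most interest. A subject with an acceptable count on Day 7, a modest fall on Day 10 and recovery by Day 15 would contribute only the first and last values to the laboratory summaries. If nobody judged the fall clinically significant, the trial database would hold no trace of it. That judgement is made by the investigator in an open-label trial.

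**Working it through.** The protocol states no figure for this gap, so there is none to reproduce. The check counts days against the schedule.

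**Inputs.** Last scheduled dose: Day 5 (synopsis). Scheduled lab days: 1 to 7 and 15 (Section 9.5, Appendix A). Day 15 window: 15 − 2 = Day 13 to 15 + 2 = Day 17 (synopsis, Section 9.5). Discharge-day samples: Sections 3.9 and 8.5.

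**1. Gap for a subject in hospital throughout.** With the final visit on day v, the days strictly between Day 7 and the visit number v − 7 − 1.

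| Final visit on | Days without scheduled collection | Count |
|---|---|---|
| Day 13 | 8-12 | 13 − 8 = 5 |
| Day 15 | 8-14 | 15 − 8 = 7 |
| Day 17 | 8-16 | 17 − 8 = 9 |

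**2. Position relative to dosing.** Day d is d − 5 days after the last scheduled dose. Day 8 gives 3 and Day 14 gives 9, so the nominal gap covers days 3 to 9 after dosing ends.

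**3. Share of post-dosing follow-up.** Days 6-15 are 15 − 6 + 1 = 10 days. Scheduled collection falls on Days 6, 7 and 15, so 10 − 3 = 7 have none. This assumes that daily testing does continue to Day 7. The rule lets the clinician stop it sooner.

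**4. What the discharge rules add.** A discharge-day sample on day d splits the nominal gap into d − 8 days before it and 14 − d days after it.

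| Discharge on | Before | After |
|---|---|---|
| Day 10 | 2 | 4 |
| Day 11 | 3 | 3 |
| Day 12 | 4 | 2 |

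Discharge on Days 13-15 brings the final-visit activities forward. Discharge on Days 8-9 is covered in the brequinar arm by Section 3.9. For the standard-of-care arm no paragraph clearly applies: the sentence in Section 8.5 addressed to all subjects sits in the paragraph on discharge before Day 5, and the next paragraph starts at Day 10.

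**5. What the adverse-event route adds.** It has no gap on Days 8-14. Section 10.8 makes clinically significant out-of-range results adverse events, and Section 10.1 has Grade 3 or 4 toxicities re-evaluated every 2 days as feasible. What escapes is a value that is not judged clinically significant, causes no signs or symptoms and needs no therapy. Adverse-event terms also do not give the depth and timing of a fall in the form needed for a summary by arm.

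**6. Effect of the change.** If results in the record were collected through Day 15 or discharge, the nominal 7-day gap for a continuing in-patient would fall to 0, to the extent that tests were actually done.

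**The case against.** The strongest reply is that the adverse-event component already covers what matters. It runs without interruption through Day 15, takes in clinically significant laboratory results, and also takes in a pre-existing abnormal finding that changes in severity after dosing. Unscheduled tests are permitted, and bleeding signs are asked about specifically. The prior experience cited at this dose level is one mild thrombocytopenia among 39 subjects (Section 3.6.2), with events followed through 21 days (Section 8.2.1). On this view the rest is a preference about collection frequency. Most of this stands, and it limits the point to falls that do not become adverse events.

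Four stronger readings are tempting, and the documents do not support them.

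- A reader might infer that no laboratory value from Days 8-14 ever enters the trial. Sections 3.9 and 8.5 bring in discharge-day samples, and the final-visit window opens on Day 13.
- A reader might infer that a marrow effect in this period is missed by the primary endpoint as a whole. Only the laboratory component has the gap.
- A reader might infer that the DSMB and the Medical Monitor cannot see these counts. Section 10.8 gives both the available hematology data without a day limit, and Section 13.3 allows sponsor personnel access to the electronic record.
- A reader might combine the ±2-day windows in Section 10.8 into a gap from Day 5 to Day 17 (17 − 5 = 12 days). That concerns subjects already discharged, whom collection from the in-patient record cannot reach.

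It is also not certain that the values exist. Section 10.8 expects daily in-patient counts, but Section 9.5 lets the clinician end daily testing.

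**Conclusion.** The point holds in a limited form. For subjects who remain in hospital, nothing schedules the collection of routine hematology/chemistry between Day 7 and the Day 15 visit: 7 days nominally, 5 to 9 with the window. A transient fall in that interval that does not qualify as an adverse event would be absent from the laboratory component of the primary endpoint, and its depth and timing could not be summarised by arm.

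This rests on two assumptions: that standard-of-care tests are still being drawn after Day 7, which Section 10.8 makes likely but not certain, and that an effect could fall in the window. The documents give no time to nadir and do not establish that brequinar produces one on Days 8-14. The case for change is that the information probably exists, bears on the toxicity the protocol singles out, and is cheap to record. It is not that harm is known to be hidden.

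**What to change.** In Section 9.5 (Days 1-7 and the final visit), the matching synopsis text and Appendix A, ask sites to collect all hematology/chemistry results available in the electronic record through Day 15 or discharge. State that no additional draws are required, which keeps to the Appendix A instruction against drawing a second set of labs.

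**Cost.** More data entry for subjects still in hospital after Day 7, in a trial of about 24. There are no extra visits or samples.

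**Downside.** The Days 8-14 values would come only from subjects still in hospital and still being tested, a group defined after randomization, and should be labelled as such. A worst value tends to become more extreme with more draws, so any such comparison between arms has to be read alongside the number of draws and the length of stay.

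Two sets of passages also need reconciling:

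- The discharge-day sample rules in Section 3.9 (brequinar arm only) and Section 8.5, which together leave standard-of-care subjects discharged on Days 8-9 without a clear rule.
- The Day 7 laboratory window, which is ±2 days for early-discharged brequinar subjects in Section 10.8 and ±8 hours in Section 9.5 and Appendix A. The Section 10.8 window may be meant specifically for outpatients. If so, the protocol should say so.
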